			Amended Table of contents to capture changes in page numbering.

2 Synopsis

[figure not shown]
Short title	RODEX: A multicentre, randomized, open-label study of romiplostim plus dexamethasone vs dexamethasone in patients with newly diagnosed primary immune thrombocytopenia					
Acronym	RODEX					
Clinical phase	Phase III					
IRAS number	1007244					
EudraCT ref	2021-00690-22					
ISRCTN ref	TBC					
IRAS number	1007244					
Funder	Andalusian Public Foundation for Health Research Management of Seville (FISEVI), Spain. IMP and distribution provided for free by the drug manufacturer, Amgen.					
CTR Study Number	1227					
Trial design	Open label, randomised, Phase 3 study to compare romiplostim plus dexamethasone vs dexamethasone alone in terms of sustained response off any ITP treatment in adult subjects with newly diagnosed ITP.					
Trial participants	Adult patients with newly diagnosed ITP and a clinical indication for first line treatment					
Planned sample size	Total: 126; UK (England, Wales and Scotland): 26+					
Planned number of sites	UK: 10-15					
Duration:	Total: 36 months Treatment: Up to 2 years Follow-up: Up to 1 year from date of last dose of IMP First patient inclusion: Last quarter 2022 Last patient inclusion: First quarter 2024 Subject participation duration: 24 months					
Inclusion criteria	 ≥18 years old at time of informed consnet New diagnosis of primary ITP Platelet count <30x10⁹/L or ITP with platelet count <50x10⁹/L and concomitant bleeding symptoms Serum creatine concentration ≤1.5 mg/dL 					
Exclusion criteria	 WHO performance status >2 Previous therapy with rituximab (within 3 months previous of study enrollment), corticosteroids or therapy with other immunomodulating agents within 1 month before enrolment; prior use of hematopoietic analogs or fostamatinib for any other reason than ITP three months before enrolment. Previous use of romiplostim, PEG-recombinant human (rHu) 					
	megakaryocyte growth and development factor, eltrombopag, recombinant human antithrombopoietin (rHuTPO), or any platelet-producing agent for three months prior to enrolment. 4) Alkylating agents within 8 weeks before the screening visit or anticipated use during the time of the proposed study.					

- 5) Splenectomy within 3 months of the screening visit or planned splenectomy during study period.
- 6) Abnormal renal function (serum creatinine > 1.5 mg/dL).

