- 23) Female subject of childbearing potential is not willing to use, in combination with her partner, an acceptable method of effective contraception during treatment and for 1 month after the end of treatment (see annex 5 for additional contraception information). Females of childbearing potential should only be included after a negative pregnancy test.
- 24) Will not be available for protocol-required study visits, to the best of the subject's and investigator's knowledge.

[figure not shown]
	25) Any kind of disorder that, in the opinion of the investigator, may compromise the ability of the subject to give written informed consent and/or to comply with all required study procedures.26) Other serious comorbidities at investigator criteria.						
Primary objective	To evaluate the superiority of romiplostim plus dexamethasone vs dexamethasone alone in patients with newly diagnosed primary immune thrombocytopenia (ITP) in terms of sustained response off any ITP treatment (6 months (≥180 days) from treatment cessation, 6mSROT-50) and without WHO grade 2 or more bleeding.						
Secondary objectives	Multiple as described in Main Protocol						
Primary outcomes	To evaluate the difference between study achieving 6mSROT-50 at 6 months (180 da						
Secondary outcomes	Multiple secondary outcomes as detailed i	in Main Protocol.					
Investigational medicinal products (IMPs)	Dexamethasone (DEX) Romiplostim (ROM) (comparator drug) (investigational drug)						
Manufacturer	TAD Pharma, UK	Amgen, UK					
EU Certification, Labelling	Alcura Health, Spain	Alcura Health, Spain					
UK Import and Distribution	Alcura Health, UK	Alcura Health, UK					
Form	Uncoated tablets (4 or 12 per blister pack)	5mL single-use vial of sterile, preservative-free, lyophilised, solid white powder for resuspension					
Dose	40 mg daily: Investigational arm: X 4 days only in the first cycle and subcutaneous romiplostim weekly (ROM + DEX arm) for up to 12 months Comparator (DEX arm): Dexamethasone 40 mg daily x 4 days for up to 3 cycles every 14 to 28 days	Starting dose of 3 mcg/kg calculated on current body weight. Adjusting the following doses according to platelet counts.					
Route	Oral taken at home by participant	Subcutaneous injection					
Storage	Below 25°C. Protect from light and humidity.	2-8°C. Protect from light.					
Routine rescue medication	IVIg, platelet transfusion or prednisone. Tranexamic acid can be used but is not considered a rescue medication (excluded).						

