12.4 Bleeding Events

Bleeding will be assessed by Site at every visit. Events will be assessed using WHO grading. ITP-specific bleeding using the ITP-BAT tool at the timepoints specified in the Main Protocol. All bleeding data will be entered remotely on the relevant section of the EDC System by Sites.

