13.2 SAE and Quality Complaints Reporting

See Main Protocol Section 11 for SAE and Quality Complaint reporting procedures.

Serious Adverse events (SAE) should be graded using the NCI Common Terminology Criteria for Adverse Events (CTCAE) Version 5.0 and reported using the RODEX SAE Reporting Form.

The PI (or delegated medically qualified doctor from the trial team) should sign and date the form following procedures specified in the Main Protocol to acknowledge that he/she has performed the seriousness and causality assessments. Investigators should also report SAEs to their own health boards or trust in accordance with local practice.

All adverse events should be reported from time of signature of informed consent, throughout the treatment period up to, and including 30 days after the participant receives their last dose of the IMP. Serious adverse reactions (SARS; such as long term side effects of trial treatment under investigation) should continue to be reported until the end of follow up as defined in the protocol.

The participant will be identified on the SAE form by trial number, age (year/month/day), age group, full date of birth and (if applicable) full date of death only. The participant's name (or any other personal identifiers) should not be used on any correspondence with the Sponsor and/or CTR, i.e. reported in pseudonymised format. The participant will be identified to the CTR via trial number only.

Minimum reporting data fields and reporting timeframe restrictions are specified in the Main Protocol.

Sites must respond to and clarify any queries raised by the Sponsor on any reported SAEs and report any additional information as and when it becomes available through to the resolution of the event. Additionally, drug companies may request additional information relating to any SAEs/SARs and the site should provide as much information as is available to them in order to resolve these queries.

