22.2 Audits & Inspections

The UK CI or PI organisations/institution(s) will permit trial-related monitoring, audits, REC/ IRB review, by relevant EU and UK regulatory bodies, Sponsors and CROs (inclusive of the CTR) and providing direct access to source data/documents for these organisations for EU and UK clinical trial regulatory purposes as specified in the Main Protocol.

The CI or PI organisations/institution(s) will permit trial-related monitoring, audits, REC/ IRB review,

and regulatory inspection(s), providing direct access to source data / documents.

The site must inform the CTR of any MHRA inspections.

23 Public Involvement and Engagement

Members of the public have reviewed the study where required under Sponsor and funder

procedures and policies. The CTR Study Adoption Group includes a lay member and has reviewed

and adopted the study into the CTR study portfolio. The Spanish and UK REC review panels will

include members of the public.

24 Publication Policy

All publications and presentations relating to the trial will be authorised by the Trial Management

Group and Sponsor following publication details provided in the Main Protocol.

UK sites must follow any publication restrictions specified in the UK mNCA between UK Sponsor and

Site.

Study results will be uploaded to relevant trial databases and disseminated to participants in the UK

via the UK sites and/or the CTR-hosted study website (https://www.cardiff.ac.uk/centre-for-trials-

research) as relevant.

25 Milestones

The study opened to recruitment in the lead site (Spain) December 2022. The last study patient is

anticipated to be recruited by the first quarter of 2024. The 12 month treatment phase will be followed

by a non-interventional 12 month follow-up period which will continue for up to one year after the

last participant completes protocol treatment. Each participant will remain on study for up to 24

months.

The UK Sponsor aims to open and close the study to recruitment in the UK in 2023 and 2024

respectively, and to complete UK patient follow up by 2025.

A study calendar describing overall study milestones is provided in the Main Protocol.

Page 38 of 40

RODEX UK Protocol Addendum V2.0 17.08.2023 FINAL Authorised CLEAN

TPL/003/1 v5.0, 26/10/2022

26 References

- Common Terminology Criteria for Adverse Events (NCI CTC) V5.0
- WHO / ECOG Performance Status
- Dexamethasone trial drug label
- Romiplostim trial drug label
- Dexamethasone SPC
- Romiplostim SPC

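### All-cause adverse event reporting stops 30 days after the last IMP dose, so its length depends on the arm and no all-cause control rate exists after about month 3

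*Protocol*

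**What the plan says.** Section 13.2 sets one reporting rule for both arms. All adverse events are reported from consent "throughout the treatment period up to, and including 30 days after the participant receives their last dose of the IMP". The next sentence extends one class only: serious adverse reactions "should continue to be reported until the end of follow up as defined in the protocol".

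The Dose row of the synopsis (Section 2) gives the treatment lengths. Control is "Dexamethasone 40 mg daily x 4 days for up to 3 cycles every 14 to 28 days". The investigational arm has dexamethasone in the first cycle only and "subcutaneous romiplostim weekly (ROM + DEX arm) for up to 12 months".

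Section 14.2 states that the trial is open label, and Section 13.2 has the site's doctor make the causality assessment. Section 12.4 handles bleeding separately: "Bleeding will be assessed by Site at every visit". Section 10.1 keeps participants who stop treatment on the visit schedule unless they withdraw consent to it, die or are lost. Section 3.3 lists visits at week 8, week 12, month 6, month 12 and end of study, with slight differences by arm.

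The document is not consistent on treatment length. The Duration row of the synopsis has "Treatment: Up to 2 years", against up to 12 months in the Dose row and a 12-month phase in Section 25 ("The 12 month treatment phase will be followed" by 12 months of follow-up). Sections 13 and 13.2 refer to the Main Protocol, which is not shown, for full safety procedures and reporting timeframes.

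**The concern.** The rule is worded identically for both arms, but its end point is the last dose, and the last dose falls at very different times. A control participant leaves all-cause reporting within about three months. A ROM+DEX participant can stay in it for about thirteen.

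Two things follow. Crude counts or percentages of participants with an AE or SAE would compare unequal observation periods. More importantly, events that are never recorded cannot be recovered at the analysis stage. Take a thrombosis at month 8. In a participant still on romiplostim it is reported whatever its cause. In a control participant months past dexamethasone it is reported through this route only if the site calls it related. An excess in ROM+DEX after about month 3 would then have no concurrent all-cause control rate to be judged against. The gap also works against knowledge of the control strategy: Section 3.3 says most steroid-treated patients relapse, and AEs in controls who relapse and are rescued after their window closes are not collected unless they are serious reactions.

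**Working it through.** The document states no window length, ratio or event rate, so there is no figure of its own to reproduce. The check is day arithmetic from Section 13.2 and the synopsis. The short interval from consent to day 1 is ignored in both arms.

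**Control window.** Last dose day = (cycles − 1) × gap + 4; window end = last dose day + 30.
- 1 cycle: 0 + 4 = day 4; window ends day 34.
- 2 cycles: 14 + 4 = day 18 to 28 + 4 = day 32; window ends day 48 to 62.
- 3 cycles: 28 + 4 = day 32 to 56 + 4 = day 60; window ends day 62 to 90.

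**ROM+DEX window.** With weekly doses from day 1, the 52nd dose falls on 1 + 51 × 7 = day 358. Taking the full 12 months as 365 days gives day 365. The window ends on day 388 to 395. The text says up to 12 months, so shorter courses are shown too.

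| Romiplostim duration | Last dose day | Window (days) | Ratio to 90-day control | Ratio to 34-day control |
|---|---|---|---|---|
| 2 months | 57 | 87 | 0.97 | 2.6 |
| 3 months | 85 | 115 | 1.3 | 3.4 |
| 6 months | 176 | 206 | 2.3 | 6.1 |
| 9 months | 267 | 297 | 3.3 | 8.7 |
| 12 months | 358 to 365 | 388 to 395 | 4.3 to 4.4 | 11.4 to 11.6 |

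To reach a fourfold ratio against the longest control course, romiplostim must run to day 4 × 90 − 30 = 330.

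**Effect on crude incidence.** Assume the same constant event rate in both arms, so there is no true difference. P(at least one recorded event) = 1 − exp(−rate × days / 365.25). At an assumed 0.5 per person-year:
- control, 34 days: 1 − exp(−0.0465) = 4.5%; control, 90 days: 1 − exp(−0.1232) = 11.6%;
- ROM+DEX, 206 days (6 months of romiplostim): 1 − exp(−0.2820) = 24.6%;
- ROM+DEX, 395 days: 1 − exp(−0.5407) = 41.8%.

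At an assumed 1.0 per person-year the figures are 8.9% (34 days) and 21.8% (90 days) against 66.1% (395 days).

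**Sensitivity to the stated treatment length.** If the two-year entry in the synopsis governed, the ROM+DEX window could reach 730 + 30 = 760 days, and the ratio would be 760/90 = 8.4 to 760/34 = 22.4.

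**Serious adverse reactions.** If follow-up ends at the same time from randomisation in both arms, their scheduled window is equal (ratio 1.0). Section 25 says "Each participant will remain on study for up to 24" months, without splitting by arm, but the synopsis gives follow-up as up to one year from last dose. The end of follow-up therefore needs a fixed definition before it serves as a common end point.

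**The case against.** The strongest reply is that this is a UK addendum and the full safety rules sit in the Main Protocol. No between-arm AE comparison, crude or otherwise, is stated here. A window of last dose plus 30 days follows exposure to study drug and is worded alike for both arms, and unequal windows can be handled with exposure-adjusted rates or a restricted early period in the analysis plan.

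Much of this stands. The choice of safety tables belongs to the analysis plan, and its absence here is no fault. A reader might infer that the safety comparison is simply wrong, or that ROM+DEX is bound to look more toxic. The document does not support that, because it does not say how AEs will be compared.

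A reader might also infer that nothing is collected after 30 days. That is not so: serious adverse reactions continue to the end of follow-up, bleeding is assessed at every visit, and deaths have their own form (Section 10.1). Nor is 4 to 12 times a fixed ratio. It is the ceiling at 12 months of romiplostim, and with 2 months the windows can be about equal.

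What the reply does not answer is the collection gap. Exposure adjustment needs a constant-rate assumption to stand in for missing control time, and an early-period comparison says nothing about later months. The serious-reaction route depends on an open-label causality call, so it cannot supply a background rate. If the Main Protocol sets a common window, Section 13.2 differs from it and needs aligning; if it does not, the gap is trial-wide.

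**Conclusion.** The point holds as a fault in the collection rule. Followed as written, Section 13.2 closes reporting of non-serious AEs and of SAEs judged unrelated on day 34 to 90 in control, and as late as about day 388 to 395 in ROM+DEX. The size depends on actual romiplostim duration, which the document only caps. Crude AE or SAE incidence would not be comparable when romiplostim runs long, and after about month 3 there is no concurrent all-cause control rate for these events.

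The percentages are illustrations that rest on an assumed equal, constant rate; they are not forecasts. The conclusion also assumes that Main Protocol Section 11 does not already set a longer common window.

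**What to change.** Amend Section 13.2 together with Main Protocol Section 11, so that Spain, Italy and the UK use one rule. A change in the addendum alone could make UK collection differ from the other countries.

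- Collect all SAEs and all thrombotic events, regardless of causality, from consent to the same time after randomisation in both arms, plus 30 days after last dose if later. The time point could be month 12, or the end of follow-up already used for serious adverse reactions provided it is fixed from randomisation. With month 12, the residual difference is at most 395/365 = 1.08.
- Either collect other AEs over that same window, or compare them only over a period in which both arms are under collection. For one-cycle controls that period ends on day 34, so a first-90-day comparison would not be common to all participants under the present rule.
- Reconcile the two-year treatment entry in the synopsis with the up-to-12-months entry in its Dose row and the 12-month phase in Section 25, because the window length depends on it.

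Bleeding needs no change. The cost is some extra AE and SAE entry for control participants at follow-up visits. Section 3.3 lists visits at months 6 and 12, but because it lets visits vary by arm, control attendance at them should be confirmed against the Main Protocol.

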13.3 Safety Reports

13.3.1 SARs & SUSARs

Investigator reports of suspected SARs will be reviewed immediately by the Medical Monitor or suitable delegate(s) appointed by the Sponsor as specified in the Main Protocol. Those that are identified as SUSARs will be notified by FISEVI Pharmacovigilance department directly to the international European Medicines Agency (EMA) via the Eudravigilance System (EVWEB), and to the

relevant drugs company where applicable. The Sponsor will forward SUSAR events in UK Participants to the CTR for onward reporting by the CTR to the MHRA via EU Individual Case Safety Report (ICSR) System.

13.3.2 Annual DSUR, ISR and Final Report

Safety reports will be aggregated and drafted by the Sponsor.

A list of all SARs (expected and unexpected) will be reported annually to the CTR by the Sponsor for forwarding by the CTR to the MHRA and REC, in the form of a single Development Safety Update Report (DSUR) covering both trial IMPs. This report must be submitted to UK regulatory bodies within 60 days of the anniversary of the original Agencia Espanola de Medicamentos U Productos Sanitarios (AEMPS) approval date.

The Sponsor will report a list of all SARs (expected and unexpected) and any other safety recommendations to the CTR for notification to all UK PIs annually throughout the course of the trial. This frequency may be reviewed and amended as necessary. This reporting will be done via the Investigator safety report (ISR) which will be authored by the Sponsor.

The Sponsor is responsible for uploading the end of trial summary results to EudraCT as per the commission's guidelines on posting and publication of result-related information. All SAEs and AEs will be CTCAE coded or MedDRA coded to support upload.

13.3.3 Urgent Safety Measures (USMs)

An urgent safety measure is an action that the Sponsor, Chief Investigator or Principal Investigator may carry out in order to protect the subjects of a trial against any immediate hazard to their health or safety. Any urgent safety measure relating to this trial will be notified by the Sponsor to the CTR for onward notification to the MHRA and REC immediately by telephone, and in any event within 3 days in writing, that such a measure has been taken. USMs reported to the CTR will be handled according to the RODEX UK Safety Management Plan and Main Protocol.

13.3.4 Pregnancy Reporting

[figure not shown]
Despite strict exclusion criteria around pregnancy, breast feeding and contraception and the anticipated low number of UK participants, there remains a very low risk that a participant (or for male participants, their female partner) will become pregnant during the study. If a pregnancy occurs, the participant (or their female partner where applicable), will be asked to provide **optional** consent via the study UK Pregnancy PIS/ICF for safety reporting of pregnancy data to the Sponsor and drug company (Amgen and/or TAD Pharma) where applicable.

Reported data may include confidential patient data belonging to the pregnant mother, and her unborn fetus and/or born child (including sex, date of birth and date of death).

This data will be collected and stored for a minimum of 25 years by the Sponsor in the interest of clinical trial regulatory compliance, and indefinitely by the drug manufacture under the mother's own consent, and parental consent provided on behalf of the born child where applicable, provided via the Pregnancy ICF.

The CTR will monitor for events of reporting confidential data belonging to a born child throughout the study, and liaise with the Sponsor to ascertain at the end of the participant follow up phase if/when there is a requirement for an application for CAG for CAGs251 and/or Scottish equivalent consent exemption as applicable (and continued REC approval) to support retention of data collected during childhood from a child born in England, Wales or Scotland beyond the date said child(ren) reach maturity to adulthood (age 16 years or over).

13.4 UK Event Reporting Flow Diagram

14 Statistical considerations

14.1 Randomisation

This is a randomised study. Participants will be randomised to one of the two trial arms by site via the computerised EDC System following consent, registration and confirmation of eligibility. A paper backup randomisation procedure will be used if the EDC System is inaccessible for any reason. The Sponsor is responsible for monitoring randomisation.

14.2 Blinding

This is an open label study. The participant and their treating team and GP will know which trial arm the participant has been assigned to. The study statistician and suitable delegate(s) responsible for analysis will be blinded to the results until the study analysis has been conducted in the interest of bias prevention.

14.3 Analysis

Study analysis will be delegated by the Sponsor to the Statistics and Methodology Unit, HUVR, Spain.

15 Data Management

As described in the Main Protocol, trial data, including registration, randomisation, consent and withdrawal data, will be collected via remote data entry by site into the study-specific Electronic Data Capture (EDC) System using the Open Clinica software platform.

The Sponsor has delegated development, hosting, and management of the EDC System to EFFICE Servicios Para La investigación S.L., Madrid, Spain.

The EDC will be accessed at the following web address:

https://www.efficecrf.com/OpenClinica

Individual log-in details will be provided by Effice to the CTR and/or Site as required, e..g upon site activation.

A study-specific Open Clinica Investigator Guideline, inclusive of login, support and user instructions, will be provided to sites prior to activation to recruitment and data capture.

The CTR will liaise with UK sites, EFFICE, and the Sponsor to ensure data is completed, queried and amended as per the requirements of the trial and in a timely manner via restricted access to the EDC System.

The CTR UK Data Management Plan and Monitoring Plan, and agreement between Sponsor and

National Coordinator, will document CTR monitoring activities and responsibilities.

For further information about data management refer to the Main Protocol.

16 Translational research or sub-trial – not applicable

17 Protocol/GCP non-compliance

The CTR RODEX SOP List will document if/when CTR and/or Sponsor SOPs will be followed to support

delivery of the study in the UK. A CTR SOP exemption form will be completed where applicable.

The Principal Investigator should report any non-compliance to the trial protocol or the conditions and

principles of GCP to the CTR in writing as soon as they become aware of it using the relevant form

provided by the Sponsor, for onward reporting by the CTR to the Sponsor.

18 End of Trial definition

The end of the trial is defined as the date of final data capture to meet the trial endpoint. In this case

end of trial is defined as the date of the hard data lock of the EDC, i.e. date of last visit and data

capture.

The CTR will, on behalf of the UK National Coordinator and Sponsor, notify the MHRA and main REC

of the end of the trial within 90 days of its completion or within 15 days if the trial is terminated early

and submit the final REC and MHRA reports within UK regulatory reporting timeframe requirements.

19 Archiving

The CTR, on behalf of the UK National Coordinator and Sponsor, will be responsible for archiving UK

trial documentation. Documents specifically relating to the approval and conduct of the trial in the UK

are considered essential UK TMF documents and will be archived at an approved external storage

facility by the UK lead organisation for a minimum of 25 years.

A copy of the UK TMF will be provided to the Sponsor following study closure in the UK as specified in

the agreement between the Sponsor-UK National Coordinator.

Page 33 of 40

RODEX UK Protocol Addendum V2.0 17.08.2023 FINAL Authorised CLEAN TPL/003/1 v5.0, 26/10/2022

The Principal Investigator at UK sites is responsible for archival of the local study ISF at site on approval

from the CTR on behalf of the UK National Coordinator and Sponsor. Essential documents pertaining

to the trial shall not be destroyed without permission from the Sponsor.

20 Regulatory Considerations

The Sponsor is responsible for EU regulatory submissions. Refer to Main Protocol for EU regulatory

details.

The Sponsor has delegated the role of managing UK regulatory submissions to UK National

Coordinator and CTR.

This trial has Clinical Trials Authorisation (CTA) from the UK Competent Authority (MHRA).

The Main Protocol and this UK Protocol Addendum have approval from a Research Ethics Committee

(REC) that is legally "recognised" by the UK Ethics Committee Authority for review and approval, and

will be submitted through the relevant permission system for global governance review dependant

on the location of the lead site e.g. HRA (England) and devolved equivalents (Wales and Scotland).

Approval will be obtained from the host care organisation in the UK who will consider local governance

requirements and site feasibility. The Research Governance approval of the host care organisation

must be obtained before recruitment of participants within that host care organisation.

